6.2 Secondary Outcome Measures

Outcome	Measure	Time Points
Comprehensive Physical Function	Short Physical Performance Battery (SPPB). Composite score (0-12) based on standing balance (0-4), 4-meter gait speed (0-4), and 5-repetition chair stand time (0-4). Higher score indicates better function.	Baseline, Week 4, Week 8
Executive Function - Inhibition Control	Stroop Color-Word Test (SCW). Three parts: Word, Color, and Color-Word. Interference effect (SCW score ÷ Color score) is calculated. Lower values indicate better inhibition control.	Baseline, Week 4, Week 8
Executive Function - Cognitive Flexibility	Trail Making Test (TMT). TMT-A (numbers 1-25) and TMT-B (alternating numbers and letters). Difference (TMT-B minus TMT-A) is calculated. Smaller differences indicate better cognitive flexibility.	Baseline, Week 4, Week 8
Falls Efficacy	Modified Falls Efficacy Scale (FES). 16-item questionnaire (0-10 per item, total 0-160). Higher scores indicate better falls efficacy.	Baseline, Week 8

6.3 Feasibility Outcomes

Outcome	Definition	Success Criterion
Recruitment Rate	$(\text{Number randomized} \div \text{Number screened eligible}) \times 100\%$	$\geq 60\%$
Retention Rate	$(\text{Number completed 8 weeks} \div \text{Number randomized}) \times 100\%$	$\geq 80\%$
Adherence	$(\text{Actual bouts completed} \div \text{Prescribed bouts}) \times 100\%$	$\geq 80\%$
Acceptability	5-point Likert scale questionnaire	Mean score ≥ 4
Safety	Adverse event rate	No serious adverse events

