4. STUDY POPULATION

4.1 Inclusion Criteria

1. Age 65 years or older
2. Community-dwelling (living independently, not in a nursing home or long-term care facility)
3. Pre-frail status confirmed by Fried Frailty Phenotype score of 1-2
4. Mini-Mental State Examination (MMSE) score ≥ 24
5. Able to walk independently with or without a cane
6. No regular lower limb strength training (less than 2 times per week) in the past 3 months
7. Willing to adhere to the 8-week exercise intervention and complete all assessments
8. Provide written informed consent before any study-related procedures

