4.3 Sample Size

As a pilot trial, formal power calculation is not performed. Fifteen participants per group (total N=60) will be recruited. Anticipating a 20-25% attrition rate, approximately 45 participants (11-12 per group) are expected to complete the 8-week intervention.

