8. RANDOMIZATION AND BLINDING

8.1 Randomization

- **Method:** Online random number generator (Sealed Envelope)
- **Allocation Ratio:** 1:1:1:1
- **Stratification Factors:** Sex, baseline SPPB score (3-6 vs. 7-10)

- **8.2 Blinding**

Role	Blinded?
Participants	No
Intervention Providers	Yes
Outcome Assessors	Yes
Data Analysts	Yes

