10.4 Sample Size Justification

As a pilot trial, formal power calculation is not performed. Fifteen participants per group (total N=60) will allow estimation of effect sizes (width of 95% CI for Cohen's d) and feasibility outcomes (recruitment, retention, adherence).

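### The recruitment rate in Protocol 6.3, read with inclusion criteria 7 and 8, leaves out people who refuse, so the 60% criterion does not test uptake

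*Protocol*

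**What the plan says.** Protocol 6.3 lists recruitment first among five feasibility outcomes. It is defined as "Number randomized} \div \text{Number screened eligible}) \times 100" per cent, and the success criterion is at least 60%. The document does not define screened eligible anywhere else, and no other feasibility outcome counts people approached or people who decline.

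Protocol 4.1 sets out who is eligible. Three of its criteria bear on this point:

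- Criterion 3: "Pre-frail status confirmed by Fried Frailty Phenotype score of 1-2".
- Criterion 7: "Willing to adhere to the 8-week exercise intervention and complete all assessments".
- Criterion 8: "Provide written informed consent before any study-related procedures".

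Criterion 4 adds an MMSE score of at least 24.

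On numbers, 4.3 says "Fifteen participants per group (total N=60) will be recruited". Section 10.4 gives estimation of "feasibility outcomes (recruitment, retention, adherence") as part of the reason for that size. Section 8.1 stratifies on "Sex, baseline SPPB score (3-6 vs. 7-10"), although 6.2 scores the SPPB from 0 to 12 and neither 4.1 nor 4.2 restricts entry by SPPB.

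**The concern.** A recruitment rate in a pilot is normally read as uptake: of the people who could take part, how many do. That reading needs refusals in the denominator. Here willingness and consent are entry criteria, so someone who declines fails 4.1 and is not eligible. The numerator and denominator then differ only by people lost after they have agreed and been found eligible.

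Willingness is a real uncertainty in this trial. Participants are asked to exercise daily for 8 weeks, in one arm in 15 bouts a day. If the criterion does not respond to refusals, the pilot can report recruitment as successful without having measured uptake. Refusals that were not logged during screening also cannot be reliably recovered afterwards.

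**Working it through.** The 60% is a bare threshold. The protocol gives no derivation for it, so there is no figure to reproduce. The check has three parts.

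**1. Order of events.**
- Criterion 8 puts consent ahead of any study procedure.
- Criterion 3 requires a confirmed Fried score, and criterion 4 an MMSE score. If these are obtained as study procedures, eligibility is established only after consent.
- Separately from timing, criteria 7 and 8 are themselves on the inclusion list, so a decliner does not meet that list.
- Both routes give the same result: refusals are outside the denominator.

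**2. What it takes to fail the criterion as written.** Inputs: 60 randomized (4.3) and a threshold of 60% (6.3).
- Largest number of eligible people that still passes: 60 / 0.60 = 100.
- Losses allowed: 100 − 60 = 40. The criterion fails only with more than 40 losses; for example 60/101 = 59.4%.
- Losses can arise from withdrawal before allocation, or from an SPPB of 0–2 or 11–12, which is not excluded but has no stratum in 8.1.

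Let r be the share of consented, eligible people who are randomized. The documents give no value, so a range is assumed. With 65 such people, 60% means at least 39 randomized (39/65 = 0.60). Exact binomial probabilities of passing:

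| r (assumed) | P(at least 39 of 65) |
|---|---|
| 0.70 | 0.968 |
| 0.80 | 0.9999 |
| 0.90 or more | about 1.000 |

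**3. What changes if refusals count.** Let c be the share of otherwise eligible people who are willing and consent (also assumed). As written, the expected rate is r, whatever c is. With decliners counted it is r × c. At r = 0.95, and with 100 otherwise eligible people for the probabilities:

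| c (assumed) | Rate as written | Rate with decliners counted | P(at least 60 of 100) |
|---|---|---|---|
| 0.4 | 95% | 0.95 × 0.4 = 38.0% | below 0.001 |
| 0.5 | 95% | 0.95 × 0.5 = 47.5% | 0.008 |
| 0.6 | 95% | 0.95 × 0.6 = 57.0% | 0.31 |
| 0.7 | 95% | 0.95 × 0.7 = 66.5% | 0.93 |
| 0.8 | 95% | 0.95 × 0.8 = 76.0% | 0.9999 |

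The break-even consent share is 0.60 / r: 0.67 at r = 0.90, 0.63 at r = 0.95 and 0.60 at r = 1.00.

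This table is idealized. It treats decliners as known to meet every other criterion, but their Fried and MMSE results would not exist. It shows that the rate as written does not depend on c. It does not show that 60% is the right threshold for a denominator of people approached.

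**The case against.** The strongest reply is that screened eligible is undefined. It could mean people found suitable at screening and then invited. That reading counts refusals and makes a 60% threshold sensible, and the choice of 60% may hint that refusals were expected. A site could work this way. But the protocol does not say so, and its consent-first rule and eligibility list point the other way. If both readings are in use, one log can yield two quite different rates, so the definition needs fixing in either case.

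It may also be said that such detail belongs in the SAP. The formula and the threshold are both fixed in the protocol, however, and the problem lies in what they fix.

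Several stronger inferences are tempting and are not supported:

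- *Only a change of mind can lower the rate.* Not so. People with an SPPB of 0–2 or 11–12 are eligible but have no stratum, and the documents do not say how many they would be.
- *The rate will be near 100% whatever the uptake.* That requires r close to 1, which is an assumption. The supported statement is that refusals do not move the rate.
- *The definitive trial would be planned with too few people to approach.* The protocol states no progression rule and does not say that approach numbers will be derived from this rate.
- *The 60% can simply be applied to consented over approached.* That is a different quantity, and people approached have not been confirmed pre-frail. Section 2.1 puts pre-frailty at 26.8% to 62.8% of community-dwelling older adults. Without pre-selection, 100 − 62.8 = 37.2% to 100 − 26.8 = 73.2% of those approached could be robust or frail.

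**Conclusion.** The point holds and should be corrected. Read with criteria 7 and 8, the recruitment rate in 6.3 counts only people who have already declared willingness and consented, so it does not respond to refusals. At 60 randomized, more than 40 of these people would have to be lost before randomization for the criterion to fail.

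The count of 40 follows from the protocol's own figures. The pass probabilities rest on assumed values of r and c and are illustrative. The conclusion also rests on reading eligible as 4.1 defines it, with Fried and MMSE testing treated as study procedures. That is the reading the text favours, though not the only one a site could adopt.

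**What to change.** In 6.3, state that criteria 7 and 8 do not define eligible for this outcome. Include in the denominator the people who pass the pre-consent checks in 4.1 and 4.2 that need no study testing but who decline, and record them in the screening log.

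Report the steps separately:

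1. consented / approached, where approached means people who passed those pre-consent checks;
2. confirmed eligible / consented;
3. randomized / confirmed eligible.

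Step 1 is the one that shows refusals. Step 2 shows the yield of Fried and MMSE testing, and step 3 shows losses such as withdrawal or an SPPB outside the strata.

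Before screening starts, the sponsor should state which rate the 60% criterion applies to, choosing one that counts refusals. It should also confirm that 60% suits that denominator and not carry it over automatically.

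The cost is a revised definition and one screening-log line per person approached. The reported rate will probably look less favourable.

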8. RANDOMIZATION AND BLINDING

8.1 Randomization

- **Method:** Online random number generator (Sealed Envelope)
- **Allocation Ratio:** 1:1:1:1
- **Stratification Factors:** Sex, baseline SPPB score (3-6 vs. 7-10)

- **8.2 Blinding**

Role	Blinded?
Participants	No
Intervention Providers	Yes
Outcome Assessors	Yes
Data Analysts	Yes

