10.2 Statistical Methods

Analysis Purpose	Statistical Method
Baseline characteristics comparison	One-way ANOVA or chi-square test
Within-group changes	Paired t-test or Wilcoxon signed-rank test
Between-group differences	4 × 3 mixed ANOVA, post-hoc Tukey HSD
Trend analysis	Polynomial contrast (linear, quadratic)
Effect sizes	Cohen's d (within-group), η^2 (between-group)

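### The between-group analysis omits the two factors used to stratify randomization, so between-subject comparisons lose some precision, while the group × time test is largely untouched

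*Protocol*

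**What the plan says.** - **Allocation.** Protocol Section 8.1 names the stratification factors as "Sex, baseline SPPB score (3-6 vs. 7-10", which makes 2 × 2 = 4 strata. The method is "Online random number generator (Sealed Envelope". No block size or other balancing device is given.
- **Between-group analysis.** Section 10.2 gives "4 × 3 mixed ANOVA, post-hoc Tukey HSD". Trend analysis is "Polynomial contrast (linear, quadratic", without saying whether the trend runs over arms or over visits. The baseline comparison is "One-way ANOVA or chi-square test". No row of the table names sex, SPPB category or any other covariate. Baseline enters the mixed ANOVA as one of the three visits.
- **SPPB.** Section 6.2 defines it as "Composite score (0-12) based on standing balance (0-4), 4-meter gait speed (0-4), and 5-repetition chair stand time (0-4". The primary outcomes in Section 6.1 are a 30-second chair-stand count and the Timed Up and Go.
- **Intervals.** Section 10.4 mentions a 95% interval for Cohen's d only. Section 10.2 labels Cohen's d as within-group and uses η² between groups.

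**The concern.** Stratifying on a prognostic factor is meant to remove its contribution to differences between arms. If the model then leaves the factor out, its variation stays in the between-subject error term, and the precision bought by the design is not collected.

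Some prognostic value is to be expected here. SPPB contains a timed chair stand and a gait speed, and the primary outcomes are a chair-stand count and a timed walk.

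What is at stake is the precision of comparisons of arm means. The pilot is meant to supply effect sizes for a later trial and expects only 11-12 completers per arm. The error is in the conservative direction and causes no bias.

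**Working it through.** **The plan's own figure.** Section 4.3: 60 × (1 − 0.25) = 45 and 60 × (1 − 0.20) = 48, or 11.25 to 12 per arm. The stated figure of about 45 completers reproduces. There is no power calculation to reproduce.

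**Inputs.** From the Protocol: 60 participants, four arms, three visits, four strata. Assumed, because the documents give no values: share of outcome variance explained by the strata (R²) 0.1-0.4; correlation between visits 0.7, or 0.8 where stated; strata explaining 0-20% of the variance of change.

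**Single-visit contrast.** The error degrees of freedom are 60 − 4 = 56, or 54 with sex and SPPB category added. The ratio of unadjusted to adjusted 95% interval width is t(56) / [√(1 − R²) × t(54)].

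**Mean over three visits.** At correlation 0.7 and unit variance, the variance of the mean is 0.7 + 0.3/3 = 0.8. The ratio is about √[0.8 / (0.8 − R²)]. A simulation (6,000 trials per setting, blocks of 4 within strata) gives nearly the same values.

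| R² | Single visit | Visit mean, formula | Visit mean, simulated |
|---|---|---|---|
| 0.1 | 1.05 | 1.07 | 1.07 |
| 0.2 | 1.12 | 1.15 | 1.16 |
| 0.3 | 1.19 | 1.26 | 1.27 |
| 0.4 | 1.29 | 1.41 | 1.43 |

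**Type I error.** A separate simulation (3,000 runs per setting, nominal 5%, Monte Carlo standard error √(0.05 × 0.95/3000) ≈ 0.004) had no arm effect and strata that do not predict change. With blocks within strata:

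| Test | R² | Unadjusted | Adjusted |
|---|---|---|---|
| Group main effect | 0.1 | 0.031 | 0.052 |
| Group main effect | 0.3 | 0.006 | 0.056 |
| Week 8 between arms | 0.1 | 0.032 | 0.048 |
| Week 8 between arms | 0.3 | 0.013 | 0.049 |

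At R² 0.4 and visit correlation 0.8, the unadjusted group main effect falls to 0.002. With simple randomization within strata, all unadjusted tests lie between 0.042 and 0.054.

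**Group × time.** This error term is within-subject, so stable differences between strata cancel. In the blocked runs:

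- Strata do not predict change: error mean square 0.300 with or without the factors; type I error 0.047 either way (R² 0.1) and 0.046 either way (R² 0.3). At R² 0.3, power for an assumed 0.8 SD effect in one arm at Week 8 is 0.698 unadjusted and 0.696 adjusted.
- Strata explain 10% of the variance of change: mean square 0.318 against 0.300, so standard errors are √(0.318/0.300) = 1.03 times as large. Type I error is 0.043 against 0.053, and power 0.676 against 0.709.
- Strata explain 20%: mean square 0.341 against 0.301, a standard-error ratio of 1.06. Type I error is 0.026 against 0.049.

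**Baseline-adjusted Week 8 model.** Simulated interval width without and with the strata is 1.05 and 1.04 SD at R² 0.1 (1.05/1.04 = 1.01), and 1.05 and 0.99 SD at R² 0.4 (1.05/0.99 = 1.06). Baseline already carries most of the strata's information.

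**Coverage of the SPPB strata.** The scale has 13 integer scores (0-12), and the two categories cover 8 of them (3-10). Scores 0, 1, 2, 11 and 12 have no stratum, and Section 4.1 sets no SPPB limit.

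**The case against.** A reader might infer that every between-arm test has an inflated error term. The documents do not support that. With baseline among the visits, the group × time term is the test of differential change, and it already removes stable stratum differences.

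Other points against, and what stands of them:

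- **The 7-43% figures describe a poor contrast.** They apply to means that include baseline, where no treatment effect can exist. This stands: the single-visit range of 5-29% is more relevant, and after baseline adjustment only 1-6% remains.
- **The low type I errors depend on blocking.** This stands, because Section 8.1 does not state it. Naming stratification factors has little purpose without some balancing, but that is an inference. Without blocking, only precision is lost.
- **Over-wide reported intervals.** A reader might infer that the planned intervals are too wide. The only interval named is for a within-group measure, so the point reaches only between-arm intervals such as those Tukey HSD would supply.
- **Prognostic strength is assumed.** Shared components make some correlation between SPPB and the primary outcomes likely. They do not establish an R² of 0.3-0.4 for a two-level split plus sex, and they say nothing about the cognitive or falls-efficacy outcomes.
- **Covariates could be settled in an SAP that is not shown.** An absent detail would not be a finding. Here, however, the Protocol states both the stratified design and a specific model, and the two do not match.
- **SPPB is also an outcome.** In a model with baseline among the responses, its stratum is a grouping of one of those responses. A baseline-adjusted model avoids this.

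**Conclusion.** The point holds in limited form. The model in Section 10.2 does not use the factors in Section 8.1, and comparisons of arm means lose precision as a result. The size of the loss depends on an R² that the documents do not give. Conservative testing is an additional consequence only under blocking. The group × time test is unaffected if stratum effects are constant over visits.

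A reader might go further and call the planned inference invalid. That is not supported: the direction is conservative, no bias arises, and the pilot states no power calculation. This is a minor improvement in precision, worth making because it costs almost nothing.

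**What to change.** 1. In Section 10.2, state that the between-group models, including the Tukey and polynomial comparisons across arms, contain sex and SPPB stratum as randomized. Either add stratum × time terms to the repeated-measures model, or use both as covariates in a baseline-adjusted model of Weeks 4 and 8. Main-effect terms alone do nothing for the group × time test.
2. In Section 10.3, include both factors in the imputation model.
3. In Section 8.1, define SPPB strata that cover every score an eligible participant can have, so that the covariate is defined for everyone, and state whether allocation is blocked within strata.

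Cost: with 60 participants, 2 of 56 between-subject error degrees of freedom and, with stratum × time terms, 2 × 2 = 4 of the 2 × 56 = 112 within-subject ones. No new data are needed, since both variables are already required for randomization.

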3. STUDY DESIGN

Design Overview

- **Design:** Four-arm parallel-group randomized controlled pilot trial

- **Allocation Ratio:** 1:1:1:1
- **Masking:** Assessor-blind (outcome assessors unaware of group assignment)
- **Intervention Period:** 8 weeks
- **Assessment Time Points:** Baseline (Week 0), Mid-intervention (Week 4), Post-intervention (Week 8)

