5. INTERVENTION

5.1 Four-Group Design Overview

All groups perform a fixed total daily volume of 15 repetitions per exercise (sit-to-stand, squat, and heel raise), resulting in 45 total repetitions per day. The only difference between groups is the fragmentation pattern.

Group	Repetitions per Bout (per exercise)	Bouts per Day	Duration per Bout	Fragmentation Level
G1 (Highly Fragmented)	1	15	~30 seconds	Highest
G2 (Moderately Fragmented)	3	5	~90 seconds	Moderate
G3 (Lowly Fragmented)	5	3	~2.5 minutes	Lower
G4 (Consecutive Control)	15	1	~7.5 minutes	None

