5.3 Triggering Strategies

Group	Trigger Type	Specific Instructions
G1	Event-based	Perform one bout after each bathroom visit and after each time drinking water
G2	Fixed time points	Perform bouts at approximately 9:00, 12:00, 15:00, 18:00, and 21:00
G3	Fixed time points	Perform bouts at morning (9:00), noon (14:00), and evening (19:00)
G4	Fixed time	Perform the single daily bout at a consistent time (e.g., 10:00 AM)

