5.4 Progressive Loading

Phase	Weeks	Strategy
Adaptation	1-2	Slow controlled speed, emphasis on movement quality
Stabilization	3-5	Moderate speed, increase repetitions per bout for G2 and G3
Progression	6-8	Explosive speed (sit-to-stand and squat), optional weighted vest (2-4 kg) for G3 and G4

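### Section 8.2 lists intervention providers as blinded, but whoever gives the arm-specific instructions must know the arm, so the stated protection against performance bias does not exist

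*Protocol*

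**What the plan says.** The table in Protocol section 8.2 gives a blinding status for four roles. Participants are declared unblinded ("Participants No"). Outcome assessors and data analysts are declared blinded, and so are the people who deliver the intervention: "Intervention Providers Yes".

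The design overview in section 3 has one masking line, "Assessor-blind (outcome assessors unaware of group assignment", which does not mention providers.

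Section 5.1 defines the arms by how a common daily volume is split: "The only difference between groups is the fragmentation pattern". Section 5.3 then gives each arm its own cue. For G1 it is "Perform one bout after each bathroom visit and after each time drinking water"; for G2, "Perform bouts at approximately 9:00, 12:00, 15:00, 18:00, and 21:00"; for G3, "Perform bouts at morning (9:00), noon (14:00), and evening (19:00"; for G4, one bout at a regular time of day. Section 5.4 adds steps for some arms only: more repetitions per bout for G2 and G3 in weeks 3-5, and in weeks 6-8 an "optional weighted vest (2-4 kg) for G3 and G4".

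**The concern.** A drug trial can blind the person who hands over the treatment because the tablets look alike. Here the treatment is the instruction itself, and the instruction differs by arm. The person who gives it cannot be unaware of it.

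What is at stake is performance bias: differences between arms in encouragement, attention, or the handling of easier and harder exercise variants, arising because staff know the allocation. Section 5.2 lists regressions for each exercise and section 5.4 makes the vest optional, so delivery leaves some room for judgement. The protocol does not say who exercises that judgement.

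A report that copied the table would tell readers this route to bias was closed. The abstract says the pilot is meant to inform a definitive trial, so the same masking claim could be carried into that trial's design.

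**Working it through.** No sample size, power or error rate is involved and the plan states no figure to reproduce. The check is whether the section 8.2 entry can be true given sections 5.1, 5.3, 5.4 and 6.3.

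**Step 1. What differs by arm.**

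| Arm | Repetitions × bouts per day (5.1) | Trigger (5.3) | More repetitions per bout, weeks 3-5 (5.4) | Vest option, weeks 6-8 (5.4) |
|---|---|---|---|---|
| G1 | 1 × 15 = 15 | Toilet visits and drinks of water | No | No |
| G2 | 3 × 5 = 15 | Five clock times | Yes | No |
| G3 | 5 × 3 = 15 | Three clock times | Yes | Yes |
| G4 | 15 × 1 = 15 | One regular time | No | Yes |

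**Step 2. Which items identify the arm.** The nominal daily volume is 15 repetitions per exercise in every arm, so it reveals nothing. The bout counts (15, 5, 3, 1) are four different values for four arms, so the count alone identifies the arm. The triggers are also four different instructions, so the trigger alone identifies it. The vest option only separates G3 and G4 from G1 and G2, and the weeks 3-5 step only separates G2 and G3 from G1 and G4. Neither later step identifies an arm by itself, and the argument does not need them.

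**Step 3. Whether contact after the first session also reveals the arm.** Section 6.3 defines adherence as bouts completed over bouts prescribed. The daily denominator is 15, 5, 3 or 1, so anyone who checks an exercise log (listed in section 9.1) against the prescription sees the arm. Applying the section 5.4 progression also requires knowing which arms it covers.

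**Step 4. Whether anything in the protocol would hide this.** One could imagine staff who teach only the movements in section 5.2, which are the same in all arms, while someone else issues the schedule. The protocol describes no such split and no common script or sham schedule. Even with a split, the person issuing the schedule would be delivering the intervention and would know the arm.

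**Step 5. Comparison with section 3.** Section 3 names assessors and is silent on providers. It is equally silent on analysts, whom section 8.2 also lists as blinded. The two sections differ in detail and do not contradict each other. The conflict lies between the provider row and the intervention sections.

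**The case against.** The strongest reply has four parts.

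*The providers' tasks are not described.* Sections 5.1 to 5.4 say what participants do, not who instructs them, and the bouts look largely self-administered. To call provider blinding impossible because providers teach the schedules therefore rests on an inference. That stands as a caution on wording. The inference is still a necessary one: someone must convey the bout count and the trigger, and that person knows the arm.

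*The primary tests are already protected.* A reader might infer that a provider who is counted as blinded could run the 30-second chair stand or the Timed Up and Go, and that encouragement by testers would then bias the primary outcomes. The documents do not support this. Section 3 requires assessors to be unaware of group assignment, and section 8.2 lists them as a separate blinded role, so anyone who has learned the arm through delivery is excluded by the protocol's own rule. Encouragement during testing is detection bias, which assessor blinding addresses. What remains is smaller: the separation of staff is implied and never stated, and a row calling providers blinded removes the obvious prompt to state it.

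*The vest proves little.* This stands. It is optional, confined to weeks 6-8, and shared by two arms.

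*The consequences are small.* No analysis, population or success criterion depends on provider blinding, participants are already unblinded, all four arms are active, and the trial is a pilot without a power calculation. This limits the size of the point but does not remove it. The masking statement governs how risk of bias is reported, and here it is wrong in the favourable direction.

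**Conclusion.** The concern holds as a misstatement of masking. The provider row claims blinding that the intervention, as described, rules out, so the implied protection against performance bias is absent.

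Its size can be stated only qualitatively. Each of the four arms is identifiable from the bout count or from the trigger. How far provider knowledge would move any outcome, and in which direction, cannot be derived from the document.

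The conclusion rests on one assumption: that the provider role includes conveying the schedule or overseeing its progression. If the sponsor means a role limited to teaching technique common to all arms, the protocol would need to say so and to name who issues the schedules; that person would still be unblinded.

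Two stronger conclusions should not be drawn. The error does not show that outcome assessors or data analysts are unblinded. Nor do sections 3 and 8.2 contradict each other, since the masking line in section 3 is a summary that is less detailed than the table.

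The correction is worth making before the trial is reported, because it is a plain factual error about bias protection in a pilot intended to shape a larger trial.

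**What to change.** 1. In the section 8.2 table, change the entry for intervention providers to No.
2. In sections 3 and 8.2, describe the trial in the same terms: outcome assessors and data analysts blinded, participants and providers not blinded.
3. Add one sentence stating that staff who deliver or monitor the intervention, including anyone who reviews exercise logs or video checks, do not perform the Week 4 or Week 8 outcome assessments and do not disclose the arm to assessors.

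The cost is one table entry, aligned wording in two sections and one added sentence. The masking statement becomes slightly less favourable. Blinded assessors are already planned, so the change should need no extra staff, and it alters no exercise schedule or analysis.
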